6. INVESTIGATIONAL MEDICINAL PRODUCT AND PLACEBO

6.1 STUDY DRUG

6.1.1 Study Drug Identification

Pravastatin Sodium 40mg tablets

6.1.2 Study Drug Manufacturer

The IMP (Pravastatin 40mg) will be manufactured by:

Teva UK Limited [name] [contact]

It will be supplied to ISG (Investigational Supplies Group) who will perform overencapsulation of the pravastatin, and who will manufacture the placebo to be used.

6.1.3 Marketing Authorisation Holder

Teva UK Limited, Marketing Authorisation PL-00289/0409

6.1.4 Labelling and Packaging

Medication labels will be in the local language (English) and comply with the legal requirements of Annex 13 of the European Union's Good Manufacturing Practice (GMP).

CR007-T01 v4.0 PIPIN Protocol Version 5.0 17/05/2019 Page **21** of **45**

Additional packaging for the trial will be provided by the GMP compliant company ISG and released to site by a QP. This involves overencapsulation of the IMP in 'Swedish Orange' 00 capsules, with a back filling of lactose. Placebo will be created using the excipient of pravastatin (lactose), again overencapsulated in Swedish Orange 00 capsules. 60 bottles of IMP / Placebo,each containing 7 doses will be provided. The bottles will blind labelled according to randomisation with 'Study Drug Pravastatin/Placebo, 7 capsules, Code ***' The label will have a space on which to write the participant's name..

6.1.5 Storage

The majority stock of trial drugs (including both pravastatin and placebo-containing bottles) will be stored in the local hospital pharmacy. A subset of this stock, ready for dispensing to participants, will be kept on in a locked cupboard in the clinical treatment area i.e.labour ward, from where it can be dispensed in as previously described. When stock in clinical area reaches critical levels as determined by the randomisation block size, further stock will be ordered from the local pharmacy to replenish.

Daily temperature monitoring during the working week (Monday – Friday) will occur both in pharmacy and on labour ward, and a log retained for accountability. Over the weekend maximum temperature inside the storage cupboard will be recorded.

Should the temperature rise above 30C, the IMP subjected to this will be quarantined and a risk assessment performed to assess suitability for ongoing use.

Drugs will be transported from ISG via courier.

6.1.6 Regulatory Release to Site

This will be performed by the QP from ISG, in two batches of 30 bottles. Batch one will be released prior to randomisation of the first participant, and batch 2 approximately 12 months after this. However, batch 2 may be released sooner if recruitment warrants this.

6.1.7 Destruction of Trial Drug

Destruction of trial drug will be via the local pharmacy. At the end of the 7 day intervention period, the bottles will be collected by the trial team (at the day 7 visit). Compliance will be checked by the trial team through a count of any tablets remaining. This will be recorded in the pCRF / eCRF, and the bottles then returned to pharmacy for a further accountability check. All counts should be recorded in the accountability log.

From there, pharmacy will dispose of any remaining drug after receiving confirmation to do so from the sponsor or the sponsor's delegate. Destruction will occur as per local protocol and where possible the Certificate of Destruction retained within the pharmacy file.

6.1.8 Summary of Product Characteristics (SPC) or Investigators Brochure

The Pravastatin Sodium 40mg Summary of Product Characteristics (SPC) (06/07/2016) is provided in a separate document with a cover sheet and signature page (signed and verified by the CI and Sponsor) and is filed in the TMF.

Please refer to Pravastatin Sodium SPC and simplified IMP dossier.

6.2 PLACEBO

As the principal excipient in pravastatin sodium is Lactose monohydrate 286.62mg, this will be used for the placebo. It will be formulated into a Swedish Orange hard gelatin capsule, size 00.

6.2.1 Labelling and Packaging

CR007-T01 v4.0 PIPIN Protocol Version 5.0 17/05/2019 Page **22** of **45**

Medication labels will be in the local language (English) and comply with the legal requirements of Annex 13 of the European Union's Good Manufacturing Practice (GMP). They will include storage conditions for the drug, but no information about the participant.

The Investigational Supplies Group will be packaging the placebo and labelling.

ISG

[name]

Edinburgh

[name]

The placebo will be packaged into bottles each containing 7 tablets, and the bottles will be blindlabelled led as per the active treatment described in paragraph 6.1.4.

6.2.2 Storage

See paragraph 6.1.5 for a description of storage arrangements for the placebo, which are the same as the active treatment.

6.3 DOSING REGIME

Participants will receive 1 dose orally per 24 hour period +/- 6 hours for a total of 7 days. The drug will be dispensed immediately following randomisation from the stock in labour ward and administered at 24 hour intervals or as close to this as is practicable thereafter. The maximum dose will be one tablet in 24 hours with provision for two tablets within a 24 hour period should this enable a more practical regime (i.e. if first dose is taken at 0100, we will allow second dose at either 2200 the same day, or 0700 the following). Participants will self-dispense following the first dose, and record the time taken in their individual diaries. They will be encouraged but not enforced to take the dose at the same time each day.

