5.5.2 Treatment Allocation

Drug stocks will be held by the local pharmacy department with a small supply located in a locked cupboard in the clinical treatment area i.e. Labour Ward. Following randomisation, the next sequential pack as allocated will be detailed in the accountability log and removed from the clinical treatment area supply shelf, checked out with the consenting physician and an additional member of staff, and prescribed on the inpatient drug Kardex as 'study drug pravastatin/placebo code *** 1 tablet every 24 hours.' Following dispensing, the first dose will be administered to the participant in a timely fashion.

Whilst as an inpatient, the trial drug can be dispensed either by the midwife caring for the participant as with standard prescribed medication, or by the participant herself (marked as 'self' on the Kardex). The box containing the trial drug can be stored in the locked bedside cabinet to avoid loss / missed doses. Participants will receive instructions to take one tablet each day, at the same time each day.

Administration of the drug will be discontinued after 7 days (i.e. 7 doses) of treatment or following delivery if sooner.

Should the participant be discharged prior to completion of the 7 day course, the trial medication will be prescribed on the discharge letter under 'other drug' and using the same terminology as on the medication Kardex (including pack number). The participant will be advised to continue taking the medication once daily until there are no further tablets remaining.

There will be space in the participants' daily diary to record the time of dose administration.

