6.6 OVERDOSE

Women will be advised to take one tablet only per day.

In the participant's diary, there will explicit information including contact details in the case of overdose. Should any participant take more than the prescribed dose, she will be asked to contact the obstetric triage area. She will be assessed by a member of the clinical care team

CR007-T01 v4.0 PIPIN Protocol Version 5.0 17/05/2019 Page **23** of **45**

with a member of the trial team informed as soon as possible. Bloods will be obtained for LFTs, renal function and CK, and the participant will be monitored for as long as is clinically necessary as judged by her attending obstetrician. There is no specific treatment in the event of overdose, and participants should be treated symptomatically and supportive measures instituted as required.

Following overdose, continuation of the trial drug will be a discussed between the participant, her obstetric team and the research team. Details of discontinuation of treatment will be reported in the medical notes.

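### Section 6.3 permits a second tablet 21 hours after the first, which Sections 5.5.2 and 6.6, read literally, treat as more than the prescribed dose

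*Protocol*

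**What the plan says.** Three sections of the protocol govern how often a tablet may be taken.

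- **Section 6.3 (Dosing Regime)** sets the interval and its tolerance: "Participants will receive 1 dose orally per 24 hour period +/- 6 hours for a total of 7 days". It then gives the cap and an exception in one sentence: "The maximum dose will be one tablet in 24 hours with provision for two tablets within a 24 hour period", on the ground that this may make the regimen more practical. The example reads: "if first dose is taken at 0100, we will allow second dose at either 2200 the same day, or 0700 the following". The same section asks for later doses to be spaced at, or as near as practicable to, 24 hours. It encourages a constant time of day but does not enforce it.
- **Section 5.5.2 (Treatment Allocation)** fixes the text of the inpatient prescription as "1 tablet every 24 hours" and requires the discharge letter to use the same terms. On what women are told: "Participants will receive instructions to take one tablet each day, at the same time each day".
- **Section 6.6 (Overdose)** says "Women will be advised to take one tablet only per day", and then "Should any participant take more than the prescribed dose, she will be asked to contact the obstetric triage area". A clinical assessment follows. "Bloods will be obtained for LFTs, renal function and CK", and whether to continue the trial drug is discussed between the participant, her obstetric team and the research team.

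**The concern.** The exception appears only in Section 6.3. The prescription, the participant instruction and the overdose section are all unqualified. The people applying the rule day to day may be working from those texts: the midwife from the Kardex, the discharged woman from her discharge letter, and the woman at home from her diary, which is to carry the overdose information.

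A woman offered the 2200 option under Section 6.3 would therefore be acting within the protocol and, on the plain words of 5.5.2 and 6.6, taking more than was prescribed. Two members of staff could handle the same intake differently. One would record an allowed shift. The other would start the overdose procedure, with unscheduled bloods and a conversation about stopping. What is at stake is consistent safety handling of pregnant participants, and whether the record shows an overdose or a permitted dose.

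**Working it through.** No sample size, power or error rate is involved. The check is clock arithmetic on the protocol's own example, set against each rule in turn.

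**Inputs**
- Interval and tolerance (6.3): 24 h ± 6 h, so gaps from 24 − 6 = 18 h to 24 + 6 = 30 h.
- Example (6.3): first dose 0100; second dose at 2200 the same day or 0700 the next day.
- Prescription (5.5.2): one tablet every 24 hours.
- Advice (6.6): one tablet only per day.
- Overdose trigger (6.6): more than the prescribed dose.
- Tablet strength (6.1.1): 40 mg.

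**Gaps**
- 2200 option: 22 − 1 = 21 h, which is 24 − 21 = 3 h early.
- 0700 option: (24 + 7) − 1 = 30 h, which is 30 − 24 = 6 h late.

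**Each option against each rule**

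| Rule | 2200 option (21 h) | 0700 option (30 h) |
|---|---|---|
| 6.3 tolerance, 18 to 30 h | Inside | Inside, at the edge |
| 6.3 basic cap, one tablet in 24 h | Exceeded, but expressly allowed by the provision for two | Met |
| 5.5.2 order, one tablet every 24 h | Second tablet taken 3 h before it is due | Late, but no excess |
| 6.6 advice, one tablet only per day | Two tablets on one calendar day | One tablet on each calendar day |
| 6.6 trigger, more than prescribed | Met on a literal reading | Not met |

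In the active arm the 2200 option means 2 × 40 = 80 mg within 21 h. This figure only illustrates the example, because any gap shorter than 24 h puts two tablets in some 24-hour window.

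**From the table to the conflict.** Section 6.6 does not define overdose beyond exceeding the prescribed dose. The only text that says what is prescribed is the order in Section 5.5.2, which has neither the tolerance nor the exception. Joining the two gives the literal result in the last row. Neither section refers back to Section 6.3 to prevent it.

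**The case against.** The strongest reply is that Section 6.3 is a rule followed by an exception, with a stated purpose and an example, and is not self-contradictory. That is a fair reading of the sentence, and it stands. It does not help Sections 5.5.2 and 6.6, which state the rule without the exception, so the conflict that matters is between sections.

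A second reply is that a tablet taken 3 hours early, in a course fixed at seven doses from a bottle of seven, is a change of timing and not an excess. This is a reasonable clinical reading, and it is why the overdose result is described here as literal and not as certain. But Section 6.6 speaks of one tablet per day, and the 2200 option puts two on one day, so the text leaves the matter open.

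A reader might also infer more than the protocol supports:

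- *That the shortened interval may be used at every dose, so that exposure builds up over the course.* Section 6.3 asks for later doses at or near 24-hour intervals, Section 5.5.2 asks for the same time each day, and the example concerns only the first and second doses. The protocol does not say outright that the shift is limited to that point, which is worth clarifying, but it does not describe an accelerated course.
- *That the Kardex order itself defines an overdose.* It does not mention overdose. It only supplies the prescribed dose to which Section 6.6 refers.
- *That staff could not recognise a true double intake.* Two tablets taken together or a few hours apart fall outside the 18-hour lower limit implied by the tolerance.
- *That the compliance endpoint is distorted.* Section 6.5 defines non-compliance by missed doses, not by timing, and dose times are to be recorded in the diary.
- *That the shift will be used often.* The protocol gives no frequency.

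**Conclusion.** The point holds as an inconsistency between Section 6.3 and Sections 5.5.2 and 6.6. The protocol permits a second tablet 21 hours after the first and, read literally, also treats that intake as exceeding the prescription, with a safety procedure attached.

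Its extent is limited. It arises only when the second dose comes less than 24 hours after the first; the 30-hour option is not affected. How many of the 40 planned participants would meet it cannot be estimated from the document. No analysis figure changes.

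The conclusion rests on two assumptions: that the prescribed dose in Section 6.6 means the order written in Section 5.5.2, and that a day in Section 6.6 means either a calendar day or a 24-hour period. The 2200 option places two tablets within a day under either meaning.

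It should nonetheless be corrected, because the conflicting texts decide whether a woman following the protocol is sent through an overdose pathway, and the correction costs almost nothing.

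**What to change.** The sponsor must reconcile Sections 6.3, 5.5.2 and 6.6 so that together they state:

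1. one consistent dosing rule, including whether the shift in timing applies only after the first dose; and
2. one consistent overdose trigger, worded so that it is clear whether the intake in the Section 6.3 example falls inside or outside it.

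The same wording should then go into the Kardex order, the discharge letter and the participant diary, so that staff and participants work from one text. Which rule applies, and which section gives way, is for the sponsor's clinicians; this review takes no view.

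The cost is a wording amendment to the protocol and matching changes to those three documents. It needs no additional participants, visits or samples.

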6.4 DOSE CHANGES

No dose changes are anticipated, other than withdrawal of study medication for the reasons noted above.

6.5 PARTICIPANT COMPLIANCE

Compliance will be monitored in hospital via the participants' medication Kardex where a signature from the member of staff either dispensing the drug, or observing the participant dispensing and self-administering the medication is required. Non-compliance will be defined as two or more missed doses in a 48 hour period, or a total of 3 missed doses during the treatment period.

Any reasons for non-compliance or missed doses will be documented where possible and used to identify any common themes.

Should a participant be discharged home whilst enrolled in the trial and with further IMP to be taken, the remaining tablets will be prescribed on the discharge letter as documented above in section 5.5.2. Each page of the 'participant diary' will have a specific location for recording the time the participant has taken each dose.

In the day 7 trial visit, compliance will be assessed as reported by the participant and corroborated with her diary as well as a count of the remaining tablets (if any) remaining in the dispensing bottle. Serum pravastatin levels will also be assessed during the treatment phase.

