2.2.2 Secondary Endpoints

Secondary Endpoints:

- 1) Retention, adherence and ability to collect clinical outcomes from participants
- 2) Time to delivery from presentation and gestation at delivery
- 3) Contraction frequency as monitored at presentation and from randomisation to delivery or cessation of regular uterine activity.
- 4) Maternal markers of inflammation including, but not limited to: IL-6, IL-10, IL-13, IL-17, TNFa, IL-1RA, sTNF-RI, sTNF-R2, and HO-1, as well as levels of the soluble IL-6R and the inhibitor spg130 (abbreviated hereafter to 'Inflammatory Profile')
- 5) Fetal measures of inflammation including but not limited to: (cord IL-1, IL-6, IL-8, sIL-6R and sgp130.
- 6) Adverse events (maternal and fetal)
- 7) Time from time first seen in an acute obstetric care setting to administration of trial medication as documented in the participant medical records.
- 8) Compliance with 7 days of blinded treatment
- 9) Acceptability of the trial to those who have participated
- 10) Pharmacokinetic parameters as compared with current published data
- 11) Maternal outcomes:
 - a. Proven maternal infection
 - b. Safety of intervention to mother (self-reported AEs and biochemical monitoring of liver function tests and creatinine kinase).
 - c. Pre-labour ROM
 - d. Duration, location and level of care of hospital stay following presentation with suspected preterm labour AND following delivery.
- 12) Neonatal outcomes:
 - a. Details of in utero transfers including mode of transport required
 - b. Gestational age at delivery, morbidity and mortality, birthweight, duration and location of hospital stay post-delivery and up to 28 days post EDD.
 - c. Safety of intervention

CR007-T01 v4.0 PIPIN Protocol Version 5.0 17/05/2019 Page **14** of **45**

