3. STUDY DESIGN

Type of Trial

This is a double blind randomised placebo controlled trial. We anticipate an 18 month period from first Participant recruitment, with a further 6 months for outcome ascertainment, analysis and reporting (see Figure 1, Appendix 3: study timeline for further details). Each participant will be asked to administer the intervention (pravastatin or placebo) for a total of 7 days or until delivery (whichever occurs soonest), and will be followed up until 28 days after the estimated date of delivery (EDD).

Potential participants for recruitment will be identified following presentation to acute obstetrics services with threatened preterm labour. Women at high risk of preterm labour and delivery will also be identified from Antenatal Clinics i.e. the Preterm Birth Clinic (if available locally) and provided with information regarding the trial. Should these women then develop signs and symptoms of preterm labour, it is hoped that pre-information about the trial will improve recruitment.

Duration of trial

The primary outcome (recruitment) will be measured from the first participant's first visit to 28 days post EDD of the last (40th) participant's (recorded as last participant's last visit). Monitoring of secondary outcomes will begin following consent of the first participant to EDD plus 28 days of the last participant recruited.

Treatment Phase

The total treatment phase will be 7 days for each participant, or until delivery (whichever occurs soonest). Follow up will continue until EDD + 28 days.

Outcome Measurement

On recruitment to the trial, all participants will receive a study diary. They will record adverse events, compliance with treatment and administration and exact timing of self-medication with the IMP. Contraction frequency will also be recorded, either as monitored by the clinical team caring for the participant, or the participant herself. These data will be collected daily by the participant for the duration of the intervention (7 days or until delivery, whichever occurs soonest). Diaries will be collected at the day 7 visit by the research team member conducting the visit, and transcribed to pCRF and/or eCRF. Other outcomes will be reviewed and collected from the participant's clinical medical notes.

Feedback Questionnaire

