10.2 PROPOSED ANALYSES

Measures to be reported:

Primary outcome data

1. Trial uptake: eligible participants as compared with recruitment.

Secondary Outcome Data

- 1. Routine participant demographics including past medical history and drug history
- Any additional treatments received during inpatient stay (including magnesium sulphate, antibiotics, syntocinon / other methods of induction/augmentation and steroids)
- 3. Retention, adherence and ability to collect clinical outcomes from participants
- 4. Time from presentation with threatened preterm labour to delivery of first dose of IMP.
- 5. Time from presentation to acute care and assessment services with suspected preterm delivery to delivery itself, as well as gestation at delivery
- 6. Contraction frequency during treatment course, from presentation to delivery or cessation of regular uterine activity.
- 7. Bloods: Liver function tests, creatinine kinase levels (side effects), maternal and cord inflammatory profile (see 2.2.2 for details of measures within the inflammatory profile).
- 8. Compliance with treatment
- 9. Adverse events
- 10. Acceptability of the trial following completion of the protocol
- 11. Other clinical outcomes
 - a. Maternal outcomes:
 - i. Proven maternal infection (See Appendix 4: Glossary of Terms for definition)

CR007-T01 v4.0 PIPIN Protocol Version 5.0 17/05/2019 Page **29** of **45**

- ii. Safety of intervention to mother (self-reported AEs and biochemical monitoring of liver function tests and creatinine kinase).
- iii. Pre-labour ROM
- iv. Duration, location and level of care of hospital stay following presentation with suspected preterm labour AND following delivery.
- b. Neonatal morbidity and mortality, safety of intervention, gestational age at delivery, birthweight, duration, location and level of care required following delivery. If in utero transfer occur, cause of method of transport used.
- 12. Pharmacokinetics of pravastatin

Participant uptake the study will involve a direct analysis of eligible participants presenting to acute care and assessment services compared with recruitment. Secondary outcomes 1 and 2 will be used to perform subgroup analysis and identify potential confounders between treatment and placebo arms. Outcomes 3 - 11 will be used to directly compare treatment and placebo arms of the trial, and inform design for a large scale trial in the future.

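### The non-compliance rule in section 6.5 ignores how many doses were due, so the chance of failing it rises with time undelivered and distorts the comparison between arms.

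*Protocol*

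**What the plan says.** Section 6.5 of the protocol fixes a binary classification: "Non-compliance will be defined as two or more missed doses in a 48 hour period, or a total of 3 missed doses". It does not relate the misses to the number of doses that were due.

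The number due is not constant. Section 5.5.2 says "Administration of the drug will be discontinued after 7 days (i.e. 7 doses) of treatment or following delivery if sooner", and sections 3 and 14.7 end treatment in the same way. Section 6.3 sets the interval: "Participants will receive 1 dose orally per 24 hour period +/- 6 hours for a total of 7 days". Under sections 5.5.2 and 6.3 the first dose is administered after dispensing, and women self-dispense only from the second.

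Secondary endpoint 8 in section 2.2.2 reads "Compliance with 7 days of blinded treatment". Section 10.2 lists compliance with treatment as item 8 of the secondary outcome data and then says "Outcomes 3 - 11 will be used to directly compare treatment and placebo arms of the trial". Time to delivery is itself a secondary endpoint, and the first secondary objective in section 2.1.2 asks whether pravastatin prolongs it.

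**The concern.** A fixed count of misses works as a compliance rule when everyone has the same number of chances to miss. Here the number of chances depends on how long a woman stays undelivered, which is an efficacy outcome that the drug is hypothesised to change. A woman who delivers on day 2 has almost no opportunity to meet the definition, while a woman who completes the week has six self-taken doses on which to do so.

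Two things are at stake. If many women deliver quickly, the share flagged non-compliant will look low for a reason unrelated to adherence, and this trial exists to inform the design of a larger one. If delivery times differ between arms, the compliance comparison will partly restate the time-to-delivery comparison.

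**Working it through.** The protocol gives no compliance figure, miss rate or expected time to delivery, so there is nothing to reproduce. The check asks how the stated rule behaves under stated assumptions.

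**Inputs from the protocol.** Up to seven daily doses, ending at delivery (5.5.2, 6.3). First dose given by staff (5.5.2). Failure is two misses within 48 hours or three in total (6.5). About 20 women per arm (section 3, Stopping Rules; 40 women at 1:1).

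**Assumptions.** Each self-taken dose is missed independently with probability m, the same in both arms, for m = 10%, 20% and 30%. The 48-hour limb is met by two consecutive daily misses.

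**Step 1: one woman.** With k doses due there are n = k − 1 self-taken doses. She passes with no miss, one miss, or two misses that are not adjacent:

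P(fail) = 1 − [(1−m)^n + n·m·(1−m)^(n−1) + C(n−1, 2)·m²·(1−m)^(n−2)]

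For k = 7 and m = 0.2: 0.8^6 = 0.2621; 6 × 0.2 × 0.8^5 = 0.3932; 10 × 0.04 × 0.8^4 = 0.1638. The sum is 0.8192, so P(fail) = 0.1808.

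| Doses due | 1 | 2 | 3 | 4 | 5 | 6 | 7 |
|---|---|---|---|---|---|---|---|
| m = 10% | 0 | 0 | 1.0% | 1.9% | 2.8% | 3.8% | 4.9% |
| m = 20% | 0 | 0 | 4.0% | 7.2% | 10.4% | 14.0% | 18.1% |
| m = 30% | 0 | 0 | 9.0% | 15.3% | 21.6% | 28.7% | 36.4% |

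The rise with k does not depend on these readings. If the first dose can also be missed, m = 20% gives 4% at two doses due and 22.7% at seven. If the 48-hour limb also catches misses two days apart, with dose 1 given, it is 24.6% at seven.

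**Step 2: two arms with identical adherence.** Assume a constant daily chance of delivery with a share S undelivered at day 7. The daily chance of remaining undelivered is q = S^(1/7). P(k doses due) = q^(k−1)(1−q) for k = 1 to 6, and q^6 for k = 7. Weighting Step 1 by these probabilities gives the share flagged non-compliant:

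| Undelivered at day 7 | m = 10% | m = 20% | m = 30% |
|---|---|---|---|
| 30% vs 60% | 2.5% vs 3.6% | 9.3% vs 13.6% | 19.0% vs 27.4% |
| 50% vs 70% | 3.3% vs 4.0% | 12.3% vs 14.8% | 24.9% vs 29.8% |

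In 20 women per arm the widest gap is 20 × (0.274 − 0.190) = 1.7 women and the narrowest is 20 × (0.040 − 0.033) = 0.1.

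**Step 3: the same data as a pooled ratio.** Expected doses due are 4.43 (S = 30%) and 5.68 (S = 60%). At m = 20%, doses taken over doses due is 1 − 0.2 × 3.43/4.43 = 84.5% against 1 − 0.2 × 4.68/5.68 = 83.5%. The remaining point comes only from the staff-given dose; without that dose both arms give exactly 80%.

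**Step 4: the other reading of endpoint 8.** If compliance means taking all seven doses, a woman who takes both due doses and then delivers has five untaken and fails. Early deliverers are then penalised and the bias runs the other way. This sits badly with 6.5, which counts misses within the treatment period, and with dosing ending at delivery, but no section rules it out.

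**The case against.** The effect is small: in an unpowered feasibility trial whose primary outcome is recruitment, it amounts to fewer than two women per arm, and that size rests on miss rates and delivery times the protocol does not give. This stands and limits the weight of the point.

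Section 10.2 names compliance with treatment, not the section 6.5 flag, as what is compared; section 3 describes the number of tablets taken, and the analysis plan may choose another summary. That is fair. However, 6.5 contains the only definition the protocol gives, so the comparison inherits it unless the text says otherwise.

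Three stronger readings are tempting and are not supported.

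- A reader might infer that a woman who took nothing could pass as compliant. With one dose due the wording allows it, but that dose is the one staff administer.
- A reader might infer that capsules left after early delivery are scored as missed doses, because section 6.1.7 says "Compliance will be checked by the trial team through a count of any tablets remaining". No section equates a leftover capsule with a missed dose. Section 6.5 uses the count alongside the woman's report and diary, and a missed dose is naturally one that was due. A single capsule not yet due at the day 7 visit would not trigger either limb.
- A reader might infer that the rule records adherence falsely. It does not: a woman who misses three due doses did miss them. The fault is that flagged shares are not comparable between groups with different exposure.

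**Conclusion.** The point holds as a definition fault of modest size. The protocol states a rule whose failure probability rises with time undelivered under every variant checked, and it lists compliance among the outcomes compared between arms. If pravastatin prolongs pregnancy as hypothesised, equal adherence will tend to flag more women on pravastatin, by about 0.1 to 1.7 women per arm of 20 in the scenarios run. Those sizes assume independent misses at a constant rate, a staff-given first dose and a constant daily chance of delivery. The direction assumes that 6.5 is applied to doses due before delivery; under the seven-dose reading of endpoint 8 it reverses. The documents do not support a claim that a compliance deficit on pravastatin is certain or large.

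**What to change.** Reconcile section 6.5 with endpoint 8 by stating that compliance is judged against doses due up to delivery, withdrawal or day 7, whichever comes first. For the comparison between arms, use doses taken divided by doses due, pooled by arm, either excluding the staff-given first dose or shown with and without it. Show the distribution of doses due by arm beside it.

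Do not add a per-woman percentage cut-off. With an 80% cut-off and m = 20%, one miss fails a woman with four doses due (1 − 0.8³ = 48.8%), while a woman with seven due needs two misses (34.5%), so part of the bias would turn against early deliverers.

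The existing flag can stay as a descriptive item. Completion of all seven doses among undelivered women may be described but should not be compared between arms, because that group is selected after randomisation on an outcome the drug may change.

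The cost is a wording change and one derived variable. Dose times, tablet counts and time to delivery are already collected.
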